 - If a subject is switched to a programming parameter that is not considered to be DTM-SCS nor Conventional SCS programming for a period over two weeks
 - If a subject is switched to a programming parameter that is not considered to be DTM-SCS nor Conventional SCS programming for any length of time within the 2 weeks prior to a follow-up visit.

Overall Study Success: The percentage of Individual Responders in the test group is shown to be statistically non-inferior to the percentage in the control group.

B.7.4. Secondary Endpoints

The following secondary endpoints will be evaluated:

- Comparison of the percentage of Individual Responders between the test and control groups in a statistical test of superiority over time (i.e. based on repeated measures analysis). In addition, data will be summarized at the individual time points at 3 months, 6 months, 9 months, and 12 months. This will be performed based on all observed data with treatment defined as a time dependent covariate, and additionally based on censoring data post-crossover.

- Comparison of change from Baseline in back pain score (VAS) between test and control in statistical tests of non-inferiority and superiority. This is calculated as: Change from Baseline in Back Pain VAS = Follow-up Visit Pain VAS – Baseline Pain VAS. A negative result reflects a decrease in the Pain VAS, while a positive result reflects an increase in Pain VAS. All subjects must be using the assigned programming parameters. If a subject is switched to a programming parameter that is not considered to be DTM-SCS nor Conventional SCS programming, that subject's Baseline Back Pain VAS will be used instead of Follow-up Visit VAS after the programming change has occurred for the following follow-up visit if one of the two following conditions exist:
 - If a subject is switched to a programming parameter that is not considered to be DTM-SCS nor Conventional SCS programming for a period over two weeks
 - If a subject is switched to a programming parameter that is not considered to be DTM-SCS nor Conventional SCS programming for any length of time within the 2 weeks prior to a follow-up visit.

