A 10% margin has been previously used in a similar study.¹⁶ Meeting the statistical threshold for this test based on a 10% margin should produce clinically acceptable results.

B.9.2.2 Secondary Analyses

The following *secondary endpoints* will be evaluated:

- If the primary efficacy endpoint in the test group is found to be non-inferior to that in the control group, then a secondary endpoint will evaluate whether the proportion of subjects who achieve a 50% improvement in their back pain VAS score at 3 months in the test group is superior to that in the control group. A superiority test based on the difference in proportions will be performed based on the following null hypothesis, with a one-sided p-value of 0.05 or less considered evidence of statistical significance.

H_0 : The proportion of subjects (P) who achieve a 50% improvement in their back pain VAS score at 3 months in the Test group is less than or equal to that in the Control group.

$$P_{\text{Test}} \leq P_{\text{Control}}$$

H_1 : The proportion of subjects (P) who achieve a 50% improvement in their back pain VAS score at 3 months in the Test group is greater than that in the Control group.

$$P_{\text{Test}} > P_{\text{Control}}$$

- Change in mean VAS will be evaluated with two-sample t-test of non-inferiority in means with a 0.65 cm margin at 3 months.

H_0 : The change (C) in subject's VAS pain intensity score relative to baseline at the Primary Efficacy Assessment in the Test group is inferior to that of subjects in the Control group (active control).

$$C_{\text{Test}} \geq C_{\text{Control}} - 0.65 \text{ cm}$$

H_1 : The change (C) in subject's VAS pain intensity score relative to baseline at the Primary Efficacy Assessment in the Test group is not inferior to that of subjects in the Control group (active control).

$$C_{\text{Test}} < C_{\text{Control}} - 0.65 \text{ cm}$$

The non-inferiority margin of 0.65 cm was selected based on a previous study of a similar therapy against traditional SCS¹⁶. In that study, the experimental therapy showed a 4.9 point improvement while traditional SCS showed a 3.6 point improvement for a difference of 1.3 points. Taking 50% of this treatment effect yields the margin of 0.65.

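### The back pain VAS non-inferiority hypotheses have the wrong sign on the margin, so as printed they require DTM-SCS to be better by more than 0.65 cm

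*Combined protocol and SAP*

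**What the plan says.** Section B.7.4 lists this secondary endpoint: "Comparison of change from Baseline in back pain score (VAS) between test and control in statistical tests of non-inferiority and superiority". It defines the variable as "Change from Baseline in Back Pain VAS = Follow-up Visit Pain VAS – Baseline Pain VAS" and adds: "A negative result reflects a decrease in the Pain VAS, while a positive result reflects an increase in Pain VAS".

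Section B.9.2.2 specifies the test: "Change in mean VAS will be evaluated with two-sample t-test of non-inferiority in means with a 0.65 cm margin at 3 months". The null, described in words as the test group being inferior, is printed (formula markup as extracted) as "C_{\text{Test}} \geq C_{\text{Control}} - 0.65 \text{ cm". The alternative, described as not inferior, is "C_{\text{Test}} < C_{\text{Control}} - 0.65 \text{ cm". In plain notation:

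- H0: C_Test ≥ C_Control − 0.65 cm
- H1: C_Test < C_Control − 0.65 cm

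The margin comes from a previous study in which "the experimental therapy showed a 4.9 point improvement while traditional SCS showed a 3.6 point improvement for a difference of 1.3 points". The plan continues: "Taking 50% of this treatment effect yields the margin of 0.65".

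**The concern.** A non-inferiority margin is an allowance: the new treatment may be worse by up to that amount and still pass. For an outcome where lower is better, the allowance has to be added to the control mean. Here it is subtracted, so it becomes a hurdle that DTM-SCS must clear on the favourable side. That is a test of superiority by a margin under a non-inferiority label.

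Two consequences follow. An analyst who codes the printed hypotheses could report that non-inferiority on back pain VAS was not shown when the intended test would have shown it, possibly alongside a significant superiority result on the same outcome. An analyst who reverses the sign after the data are in would depart from the prespecified rule in the sponsor's favour, which invites challenge. This is one of only two secondary analyses in B.9.2.2 that carry a formal hypothesis.

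**Working it through.** **Step 1. The plan's own figure.** From B.9.2.2: 4.9 − 3.6 = 1.3, and 0.5 × 1.3 = 0.65 cm. The margin reproduces, and I take its size as given.

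**Step 2. Direction.** Let D = C_Test − C_Control, with C = follow-up − baseline (B.7.4). Negative D favours DTM-SCS.

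| | Null | Alternative |
|---|---|---|
| As printed | D ≥ −0.65 | D < −0.65 |
| Non-inferiority with a 0.65 cm margin | D ≥ +0.65 | D < +0.65 |

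Under the printed lines D = 0 belongs to the null, so identical treatments are classed as inferior. So is D = −0.5, where DTM-SCS is better by 0.5 cm.

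**Step 3. Could C mean something else?** Suppose C were improvement, with positive values good. The printed alternative would then say that DTM-SCS improves by at least 0.65 cm less than control, and the inequality would point the wrong way. No reading makes the words, the definition and the formulas agree.

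**Step 4. Comparison with the primary hypotheses.** B.9.2.1 also subtracts its margin (P_Test > P_Control − 10%). That is correct there, because a higher responder rate is better. In the VAS lines the inequalities were turned round but the minus sign stayed. Carry-over from the primary hypotheses is a plausible cause, but that is an inference and nothing below depends on it.

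**Step 5. Size of the effect.** Inputs:

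- n = 50 per arm, the planned minimum (B.5.5.1).
- Alpha is not stated for this test. I use one-sided 0.05, the level given for the primary test and for the responder superiority test, and 0.025 as an alternative.
- The SD of change is not in the documents. I assume 2.0, 2.5 and 3.0 cm.

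SE = SD × √(2/50) = 0.40, 0.50 and 0.60 cm. With 98 degrees of freedom the one-sided 0.05 critical value is 1.661.

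Observed D needed as printed is −0.65 − 1.661 × SE:

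- SD 2.0: −0.65 − 0.66 = −1.31 cm
- SD 2.5: −0.65 − 0.83 = −1.48 cm
- SD 3.0: −0.65 − 1.00 = −1.65 cm

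With the sign corrected it is +0.65 − 1.661 × SE = −0.01, −0.18 and −0.35 cm.

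The probability of success is from the noncentral t, with noncentrality (D − boundary)/SE. For example, with SD 2.5 and D = −1.3, it is (−1.3 + 0.65)/0.50 = −1.3 as printed and (−1.3 − 0.65)/0.50 = −3.9 corrected. Results for SD 2.0 / 2.5 / 3.0:

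| True difference | As printed | Corrected |
|---|---|---|
| DTM-SCS worse by 0.65 cm | 0.01% or less | 5% |
| Equal | 0.06 / 0.17 / 0.33% | 48.8 / 36.2 / 28.5% |
| DTM-SCS better by 0.65 cm | 5% | 94.3 / 82.6 / 69.4% |
| DTM-SCS better by 1.3 cm | 48.8 / 36.2 / 28.5% | 99.9 / 98.7 / 94.3% |

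A plain superiority test (boundary 0) at D = −1.3 and SD 2.5 has noncentrality −1.3/0.50 = −2.6 and succeeds 82.6% of the time. The printed non-inferiority test, at 36.2%, is harder to pass than superiority, which reverses their logical order.

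**Step 6. Sensitivity.** At one-sided 0.025 and D = −1.3 the figures are 36.3 / 25.1 / 18.8% as printed against 99.8 / 97.1 / 89.6% corrected. With 67 per arm (135/2, if nearly all randomized subjects contribute), SD 2.5 and one-sided 0.05, they are 44% against 99.8%.

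**The case against.** The sign error itself has no good defence. The counter-case concerns its weight.

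- **It is a secondary endpoint.** B.8.2 ties study success to the primary non-inferiority test alone and sets no success criteria for secondary endpoints. The primary hypotheses and sample size are unaffected. This stands.
- **The error is conservative.** Equal arms pass well under 1% of the time, so it cannot produce a false claim for DTM-SCS. This also stands.
- **The intent is readable.** The name of the test, the wording of both hypotheses and the margin rationale all point to non-inferiority, and only the two formula lines conflict. A careful statistician would probably notice. So the printed lines could lead to a wrong report, not that they would. But the formulas are the formal decision rule, and leaving the choice to the analyst is what prespecification is meant to prevent.
- **Other analyses cover the same outcome.** B.7.4 and B.9.2.2 also compare mean VAS change by repeated measures. That softens the practical harm. B.9.2.2 attaches no hypothesis or significance level to that comparison, so it does not replace the test.
- **The figures rest on assumptions.** SD and alpha are not given and n could exceed 50 per arm. The ranges above show that the size moves and the direction does not.
- **A separate analysis plan may differ.** B.9.2.4 refers to one for imputation details. Its text is not available here, so whether it repeats or corrects these lines is unknown.

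**Conclusion.** The concern holds. It follows from the plan's own definition of change and the printed inequalities, and needs no outside figure. The lines labelled non-inferiority specify superiority by more than 0.65 cm in the true means. To succeed, the observed advantage would have to reach about 1.3 to 1.65 cm, assuming SD 2.0 to 3.0 cm, 50 per arm and one-sided 0.05. Under the same assumptions, a true advantage equal to the cited 1.3 cm would be declared non-inferior 28% to 49% of the time, against 94% to 99.9% with the sign corrected.

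The damage is confined to one secondary test and works against the sponsor's own treatment. It still needs correcting, because a formal decision rule contradicts its label, its outcome definition and its margin rationale.

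**What to change.** In B.9.2.2 replace the two lines with:

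- H0: C_Test ≥ C_Control + 0.65 cm
- H1: C_Test < C_Control + 0.65 cm

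Repeat beside them that C is follow-up minus baseline, as in B.7.4. State the alpha for this test, which the plan does not now give. If it is one-sided 0.05, as for the other formal tests, add that success means the upper one-sided 95% confidence limit for C_Test − C_Control lies below +0.65 cm. Make the same correction in the separate statistical analysis plan if it repeats these lines.

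The cost is two signs and one or two sentences, with no change to conduct, data collection or sample size. The change should be documented before the 3-month VAS data are analysed by arm, so that it cannot be read as a response to results.

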The sample size estimate to determine primary endpoint is based on the primary objective of demonstrating non-inferiority of the test group to the control group at 3

months. Established methods were followed in determining the non-inferiority criteria and the related sample size estimate

- Test basis: Farrington-Manning binomial test for non-inferiority
- Estimated responder rate of 70% in the test group and 50% in the control group
- Significance level, alpha, of 0.05 one-sided
- Statistical power = approximately 90% or greater
- Non-inferiority margin of 10%
- Randomization: 1:1

Based on these assumptions, a minimum of 50 randomized and trialed subjects per treatment group (100 total) are required.

B.5.5.2 Overall Sample Size and Enrollment

Based on the primary endpoint requirement, a minimum of 50 subjects per treatment group are required (100 total). To account for a combined estimated attrition of 25% for subjects that do not complete the Trial Phase, and subjects that exit study before the 3-month primary endpoint visit, approximately 135 subjects would need to be randomized and trialed.

To account for 46% attrition prior to randomization (including subject ineligibility after signing the informed consent and subject dropout), it is estimated that a total of up to 250 subjects would need to be enrolled in the study.

B.5.6. Study Duration

This study is expected to last approximately 32 months. Enrollment of subjects is expected to last 18 months. Subjects who are expected to complete the study will commit to it for approximately 14 months. This consists of Baseline assessments, up to 10 days of trial stimulation, and 12 months of treatment following implantation and activation of the device.

B.5.7. Interim Administrative Analyses

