Activity	Pre-Trial Phase			Trial Phase		Permanent Implant (up to 60 days after end of trial)	Permanent Implant Phase Follow-up					
	Enrollment	Baseline	Randomization	Start Trial Phase	End Trial Phase (up to 10 days after start of trial)		Device Activation (0-14 days after implant)	1-month visit (±15 days after activation)	3 months visit (±21 days after activation)	6 months visit (±31 days after activation)	9 months visit (±31 days after activation)	12 months visit (±45 days after activation)
Informed Consent	X											
Pain Intensity Evaluation (VAS)	X				X			X	X	X	X	X
Medication Use	X	X		X	X	X	X	X	X	X	X	X
Medical/Surgical History	X	X										
Eligibility Criteria Evaluation	X											
Disability Assessment (ODI)	X							X	X	X	X	X
Quality of Life Assessment (EQ-5D-5L)		X						X	X	X	X	X
Randomization			X									
AP/Lateral x-ray imaging				X	[X]	X	[X]	X	[X]	[X]	[X]	[X]
Paresthesia Questionnaire								X	X	X	X	X
Patient Global Impression of Change								X	X	X	X	X
Subject Satisfaction								X	X	X	X	X
Adverse Event Monitoring	X		X	X	X	X	X	X	X	X	X	X
Device Programming				X		X	[X]	[X]	[X]	[X]	[X]	[X]
Device Log								[X]	[X]	[X]	[X]	[X]
Cross over									[X]			
Study Completion					X ^a							X

^a For subjects that do not have a successful Trial Phase.

[X] Optional activity.

B.9.2. Statistical Analysis

Descriptive statistics will be used to summarize baseline and outcome data collected during the study. Continuous variables will be summarized using means, standard deviations, and ranges. Categorical variables will be summarized in frequency distributions. Repeated measures models will account for within subject correlation by use of a compound-symmetric covariance structure (based on logistic regression/generalized estimating equations for binary variables, and linear repeated measures models for continuous variables).

B.9.2.1 Primary Analyses

The *primary efficacy endpoint* will be evaluated with a Farrington-Manning binomial test for non-inferiority with a 10% margin at the one-sided 0.05 alpha level.

H_0 : The percentage of subjects (P) who achieve a 50% improvement in their back VAS pain score at 3 months in the Test group is inferior to that in the Control group.

$$P_{\text{Test}} \leq P_{\text{Control}} - 10\%$$

H_1 : The percentage of subjects (P) who achieve a 50% improvement in their back VAS pain score at 3 months in the Test group is not inferior to that in the Control group.

$$P_{\text{Test}} > P_{\text{Control}} - 10\%$$

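### The month-3 VAS non-inferiority test has no gate, stated alpha or place in a testing order, so a nominal VAS claim stays available after a failed primary

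*Combined protocol and SAP*

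**What the plan says.** **Primary test.** B.5.5.1 sets "Significance level, alpha, of 0.05 one-sided" and B.9.2.1 specifies a "Farrington-Manning binomial test for non-inferiority with a 10% margin at the one-sided 0.05 alpha level".

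**Formal secondaries.** B.9.2.2 first lists two tests with null and alternative hypotheses.
- Responder superiority at 3 months opens with a gate, "If the primary efficacy endpoint in the test group is found to be non-inferior to that in the control group", and gives a one-sided level of 0.05.
- The next bullet is VAS: "Change in mean VAS will be evaluated with two-sample t-test of non-inferiority in means with a 0.65 cm margin at 3 months". It has hypotheses and a derived margin, but no gate, no level and no rank relative to the responder test.

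**Non-formal secondaries.** B.9.2.2 then lists repeated-measures comparisons of responder rate and of mean VAS change, which carry no hypothesis and no significance level.

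**B.7.4** describes the VAS endpoint more broadly: "Comparison of change from Baseline in back pain score (VAS) between test and control in statistical tests of non-inferiority and superiority". Its closing paragraph says both secondary endpoints are analysed by repeated measures. B.9.2.2 contains no month-3 VAS superiority hypothesis.

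**Elsewhere.** B.8.2 ties study success to the primary test alone and sets no success criteria for secondary endpoints. No multiplicity rule appears. B.9.2.4 mentions a separate analysis plan only for imputation details.

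**The concern.** The plan knows how to gate a test and how to label one as non-formal. For VAS non-inferiority it does neither. The test sits among the hypothesis tests, so its result could be reported as statistically significant whatever happened to the primary, and nothing says how to report it when the primary fails. If B.7.4 is followed as written, there is also a second route to a superiority claim, sharing no alpha with the responder test.

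At stake is which secondary statements the trial may present as confirmed. A further obstacle is that the printed VAS hypotheses do not express non-inferiority, so the test cannot be put in an order until that is corrected.

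**Working it through.** **1. The plan's own figure.** Inputs from B.5.5.1: "Estimated responder rate of 70% in the test group and 50% in the control group", a 10-point margin, one-sided 0.05, "Statistical power = approximately 90% or greater", 50 per arm.
- Unpooled SE = √(0.7×0.3/50 + 0.5×0.5/50) = √0.0092 = 0.0959.
- (0.20 + 0.10)/0.0959 = 3.13, and 3.13 − 1.645 = 1.48, so power is about 93%.
- With the Farrington-Manning restricted variance, power is 92.7% and 45 per arm suffice for 90%. The stated 50 is consistent.
- One-sided 0.025 would give 87.1% at 50 per arm, so the working level is 0.05.

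**2. Two ungated tests, each at one-sided 0.05** (assumed for VAS, since the plan states no level). The chance of at least one false rejection is 1 − Φ₂(1.645, 1.645; ρ), where Φ₂ is the bivariate normal distribution function.

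| Correlation ρ | Chance of at least one |
|---|---|
| Bonferroni bound | 10% |
| 0 | 9.75% |
| 0.5 | 8.8% |
| 0.7 | 8.0% |
| 0.8 | 7.5% |
| 0.9 | 6.8% |

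**3. What correlation applies.** Trials were simulated at 50 per arm.
- Control mean change was −3.6 cm, the control improvement in the earlier study cited in B.9.2.2.
- Assumed: baseline uniform on 6 to 9.5 cm, and SD of change 2.0, 2.5 or 3.0 cm (1.91, 2.30 and 2.64 after truncation to the 0–10 scale).
- Responder status was derived from the same scores. The two superiority tests correlate at 0.78–0.81.

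**4. Equal arms, if VAS superiority is run formally.** Gated responder superiority is falsely declared in 4.5–4.6% of trials, VAS superiority in 5.0%, and either in 7.1–7.3%. A second simulation (baseline about 7.6 cm, proportional relief with mean 0.5 and SD 0.35) gives 7.2% at 50 and 7.8% at 57 per arm. VAS superiority was never declared without VAS non-inferiority, so those two tests do not add error to each other.

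**5. Both true differences at their margins.** With SD 3.0 (2.64 after truncation) and true differences of −9.6 points and +0.66 cm, the primary passes in 5.2% of trials, VAS non-inferiority in 4.8%, and either in 7.5%. The responder difference there is a shade inside its margin. The formula in step 2 at ρ = 0.8 gives the same 7.5%, and further simulation at SD about 2.5 gives 7.4–8.0%. The primary's own error stays at about 5%.

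**6. The printed sign.** B.7.4 defines change as follow-up minus baseline, so negative is better. The printed alternative is C_Test < C_Control − 0.65 cm, which requires DTM to be better by more than 0.65 cm. With equal arms it would be met in only 0.05–0.2% of trials. Steps 2–5 use the non-inferiority orientation instead.

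**7. After a fixed sequence.** With each step at one-sided 0.05 and stopping at the first failure, a false claim requires rejecting the first true null reached, so the error is at most 5%. With equal arms, simulation gives 4.5–4.6% with responder superiority second and 4.4–4.6% with VAS non-inferiority second.

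**8. Power of the candidate second step, 50 per arm.**
- Responder superiority, 70% against 50%: null SE = √(2×0.6×0.4/50) = 0.0980; (0.20 − 1.645×0.0980)/0.0959 = 0.40; power about 66%.
- VAS non-inferiority: SE = SD×√(2/50) = 0.2×SD.
  - Benefit 1.3 cm (the difference in the cited study of another therapy), SD 2.5: 1.95/0.5 = 3.9; less 1.645 is 2.26; about 99%.
  - Benefit 0.6 cm (assumed): 1.25/0.4, 1.25/0.5 and 1.25/0.6 give about 93%, 80% and 67% for SD 2.0, 2.5 and 3.0.

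**The case against.** The best defence has four parts.

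**VAS superiority may not be a formal test.** B.9.2.2 gives it no hypothesis, the close of B.7.4 sends both secondaries to repeated measures, and B.9.2.2 lists the repeated-measures VAS comparison as having no significance level. This stands. A reader might infer two parallel superiority routes, each at the full level. The documents do not establish that, and the 7–8% figure applies only if the test is run formally. Without it, equal arms leave responder superiority as the only possible false secondary claim, at about its nominal level. The two formal secondaries would then jointly exceed 5% only if responder rates were about equal while mean VAS change was about 0.65 cm worse.

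**VAS cannot rescue the study.** A reader might infer that the trial could succeed on VAS after a failed primary. B.8.2 rules that out. It does not say, however, what may be called statistically significant among the secondaries.

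**Discordance is not error.** With DTM about 6 points worse on response, VAS non-inferiority passes while the primary fails in about 7.5% of trials. With equal arms, it passes in 18–37% of the trials where the primary fails. A reader might take these as false-claim rates. They are not: in the first case the true VAS difference is about +0.35 cm, and in both cases DTM is truly inside both margins. They show only how often the reporting question would arise.

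**The margin scenario is extreme.** It needs both truths at their margins, and it mixes a primary with a secondary claim. That is fair, but it is the configuration in which error control is judged.

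**Conclusion.** The gap is real and limited. VAS non-inferiority is a formal test with no gate, level or rank, and the label removing significance levels from other secondaries does not cover it. Study success and the primary's type I error are unaffected; what is exposed is a nominal VAS claim after a failed primary.

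The chance of a false primary or VAS non-inferiority claim is about 7.5% at both margins, and never above 10%. If VAS superiority is formal, a false superiority claim has probability about 7–8% with equal arms, instead of about 5%. Adding three tests as if independent (14.3%) would overstate this, because the two VAS tests are nested.

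These sizes rest on assumptions the plan does not supply: one-sided 0.05 for VAS, the sign corrected to non-inferiority, an SD near 2.5 cm, and a correlation near 0.8. The structural point needs none of them.

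**What to change.** In B.9.2.2:

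(a) Correct the VAS hypotheses so that they express non-inferiority: H0: C_Test ≥ C_Control + 0.65 cm; H1: C_Test < C_Control + 0.65 cm, with negative change meaning improvement as in B.7.4.

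(b) State one-sided 0.05 for the VAS tests. Test them only after primary non-inferiority is met, in one prespecified sequence with responder superiority, stopping at the first failure and labelling later results descriptive. One order is primary non-inferiority, VAS non-inferiority, responder superiority, VAS superiority. Keeping responder superiority second, as the plan now has it, also holds the error at or below 5%.

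(c) Reconcile B.7.4 with the list of non-formal endpoints in B.9.2.2, stating whether month-3 VAS superiority is formal or descriptive. If descriptive, drop it from the sequence.

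**Cost.** This is wording only; 50 per arm and the 92.7% primary power are unchanged. The choice of order is the sponsor's and has a price either way. Responder superiority placed second would stop the sequence in about 34% of trials under the design rates (100% − 66%), taking the VAS claims with it. VAS non-inferiority placed second would rarely stop it if the benefit is 1.3 cm at SD 2.5. At a 0.6 cm benefit it would fail in about 7–33% of trials (SD 2.0–3.0), and that failure would then block the responder superiority claim.
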